without evidence of metastasis will be censored at the last adequate assessment prior to initiation of such therapy. (Note: if progression occurs on the same date as the start of such therapy the progression will count as an event.) Additionally patients with documented progression or death after 2 or more missing tumor assessment will be censored at the last adequate assessment prior to the missing assessments. In this study, tumor assessments are assessed every 24 weeks. Therefore, time without adequate assessment is defined as 49 weeks (allowing for a +/-1 week window for assessments). The censoring rules for the primary and sensitivity analyses of MFS are summarized in Table 7.

Analysis	Censoring Rules	Date of Censoring
Primary analysis of MFS	Patients with no baseline or no post baseline assessments who have not died within 49 weeks after randomization	Date of randomization
	Patients who were randomized but confirmed metastatic at baseline	Date of randomization
	Patients who had no confirmed metastasis and did not die prior to data cutoff date	Date of the last adequate radiographic tumor assessment prior to data cutoff date
	Patients who initiate antineoplastic therapy such as cytotoxic chemotherapy, abiraterone acetate, hormonal agents, prostate cancer vaccines, nonradioactive bone-targeting agents and systemic radiopharmaceuticals for prostate cancer, or any antineoplastic therapy without evidence of metastasis	Date of the last adequate radiographic tumor assessment prior to first use of any such therapy
	Patients with radiation therapy performed for prostate cancer-related lesions without evidence of metastasis	Date of the last adequate radiographic tumor assessment prior to the earliest use of radiation therapy
	Patients with evidence of metastasis or death after 2 or more consecutive missed tumor assessment visits	Date of the last adequate radiographic tumor assessment prior to the first missed visit date

Table 7. The Censoring Rules for the Primary and Sensitivity Analyses of MFS

MFS = Metastatic Free Survival; of note, the censoring rules are applied to MFS events by either radiographic progression, or death due to any cause without evidence of radiographic progression; of note, antineoplastic therapies according to the above search criteria undergo medical review to confirm.

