6.3.6. Time to Castration Resistance

Time to castration resistance applies only to patients receiving leuprolide treatment and is defined as the time in months from randomization to the first occurrence of radiographic disease progression by BICR, PSA progression (as defined in Section 3.2.1) or symptomatic skeletal event whichever occurs first with castrate levels of testosterone (<50 ng/dL). The latest testosterone value measured prior to or at the date of radiographic disease progression by BICR, PSA progression or a symptomatic skeletal event is used to determine if the event is a castration resistance event.

Time to castration resistance is defined as the time in months from randomization to the first castration-resistant event (radiographic disease progression, PSA progression or symptomatic skeletal event), whichever occurs first. In patients with no documented castration resistance event, the time to castration resistance will be censored on the latest date from: the date of last radiographic assessment prior to the start of any new prostate cancer therapy, the last PSA sample taken prior to the start of any new prostate cancer therapy and prior to 2 or more consecutive missed PSA assessments (if applicable), and the last visit date performed. Patients with no baseline radiographic assessment, patients with no post baseline radiographic assessments, patients with all post-baseline radiographic assessments documented as "Not Evaluable", patients with no baseline PSA, and in patients with no postbaseline PSA results, the time to castration resistance will be censored on the date of randomization.

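### SAP 6.3.6 censors time to castration resistance at randomization when one component was never usably assessed, with no exception for an event on another component: wrong as written, low impact

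*SAP*

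**What the plan says.** SAP 6.3.6 defines the endpoint, for patients receiving leuprolide, as time from randomization to the "first castration-resistant event (radiographic disease progression, PSA progression or symptomatic skeletal event), whichever occurs first". A component event qualifies only if testosterone is castrate (below 50 ng/dL), judged on "The latest testosterone value measured prior to or at the date of radiographic disease progression" or on the date of one of the other two component events.

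Two censoring sentences follow.

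- The first is limited to event-free men: "In patients with no documented castration resistance event, the time to castration resistance will be censored on the latest date from" the last scan before new prostate cancer therapy, the last PSA before new therapy and before two or more consecutive missed PSA assessments, and the last visit.
- The second has no such limit. It lists "Patients with no baseline radiographic assessment, patients with no post baseline radiographic assessments", patients whose post-baseline scans were all non-evaluable, "patients with no baseline PSA, and in patients with no postbaseline PSA results", and for all of them "the time to castration resistance will be censored on the date of randomization".

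SAP 3.2.2.6 refers back to 6.3.6 for censoring. I found no exception elsewhere in the SAP or protocol.

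**The concern.** Setting a patient to time zero suits an endpoint that depends wholly on the missing assessment. SAP 6.2.2 does this for time to PSA progression when PSA is missing, and Table 7 does something similar for MFS when scans are missing. Section 6.3.6 joins the scan and PSA versions in an endpoint with three components, so each becomes sufficient alone. Yet PSA progression needs no scan, and an SSE needs neither scan nor PSA.

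Two things are at stake. A man who met the definition on one component could be removed because another was never evaluable. A man followed validly on PSA, testosterone and SSE could contribute no time at risk. The two sentences also give different dates for the same event-free man, with no stated precedence, so two programmers could build different datasets from the same text.

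**Working it through.** The plan gives no event count, power or sample size for this endpoint, so there is no figure to reproduce. The check is to apply the rule to example patients, identify which groups can hold real events, and then bound the size under stated assumptions.

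**Step 1. Apply the rule.**

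| Patient | Last sentence, literal | Last sentence, event-free men only | Preceding sentence |
|---|---|---|---|
| A: castrate PSA progression at month 40, all post-baseline scans non-evaluable | time 0, censored | event at month 40 | not applicable (has an event) |
| B: event-free, PSA and visits to month 48, no evaluable post-baseline scan | time 0, censored | time 0, censored | censored at month 48 |
| C: one missed scan or PSA, others usable | not triggered | not triggered | usual rule |

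Patient A shows the erased event. Patient B shows the conflict, which remains on either reading. Patient C marks the limit: the trigger is complete absence of usable data on an item, not a single gap.

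**Step 2. Which of the five groups can matter?**

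- *No baseline scan or PSA.* Central screening PSA (protocol 4.1, criterion 5) and central imaging review (4.2, criterion 1; Table 1) are needed for eligibility. These groups should be nearly empty.
- *No post-baseline PSA.* Testosterone is scheduled with PSA at every visit except week 36 (protocol Appendix 5), and entry testosterone must be at least 150 ng/dL (4.1, criterion 6). With no later value the latest testosterone is not castrate, so no event can qualify. Local testosterone testing under Appendix 6 is a possible exception, though protocol 9.1.3.7 bases this endpoint on central-laboratory values.
- *No post-baseline scan, or all non-evaluable.* PSA, testosterone and SSE data can still exist. This is the practical exposure.

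**Step 3. Size, for illustration.** Enrolment is 1068 (SAP 5.1.1), allocated 1:1:1. The other inputs are assumptions.

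- Men in the two leuprolide arms: 1068 × 2/3 = 712.
- Assumed 1% to 5% in a time-zero group: 0.01 × 712 = 7.1; 0.05 × 712 = 35.6.
- Assumed 10% to 30% of these with a qualifying event: 0.10 × 7.1 = 0.7; 0.30 × 35.6 = 10.7. About 1 to 11 events are erased on the literal reading.
- Assumed mean follow-up of 4 years: 7.1 × 4 = 28; 35.6 × 4 = 142 person-years lost.

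**Step 4. Effect on the hazard ratio, by simulation.** Settings, all assumed: 356 men per arm, exponential times with control hazard 0.35/60 per month, true hazard ratio 0.60, censoring uniform over 36 to 84 months, 150 replicates, observed/expected log-rank estimate.

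| Men set to time zero | Estimated HR |
|---|---|
| none | 0.60 |
| 5% of both arms, unrelated to outcome | 0.59 |
| 18 event patients, control arm only (18/356 = 5%) | 0.68 |
| 18 event patients, experimental arm only | 0.46 |

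Balanced loss hardly moves the estimate. The last two rows are deliberately extreme: every affected man has an event and all are in one arm.

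**The case against.** **The sentence may be meant for event-free men only.** The limit could carry over from the sentence before. The Table 7 footnote says that for MFS "the censoring rules are applied to MFS events by either radiographic progression, or death due to any cause" without radiographic progression; 6.3.6 has no such statement, which gives this reading some support. The footnote also shows that this SAP does let censoring override events, so it does not settle the matter. For patient B it makes no difference.

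**Time-zero censoring is the SAP's convention, and a never-scanned man's radiographic status is unknown.** That is a fair argument for an endpoint based on one assessment. The SAP's own neighbouring endpoints do not follow it: symptomatic progression, also a composite, is censored at the last visit (6.3.7), and SSE at the later of last visit and randomization (6.3.8).

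**Table 7 is not a general model.** This stands. Its time-zero row covers "Patients with no baseline or no post baseline assessments who have not died within 49 weeks after randomization", which exempts early deaths only, not early events of every kind.

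**Few men can be affected.** This also stands. PSA progression counts only on active treatment (SAP 6.2.2), when scans are scheduled at week 25, week 49 and every 24 weeks thereafter. Men who leave treatment early have no scheduled PSA or testosterone in long-term follow-up, while their scans continue (protocol Table 9). A man with a qualifying event or long PSA follow-up but never an evaluable scan should be uncommon.

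**The study is unblinded.** A censoring rule changed now cannot replace the planned analysis. That governs the form of the remedy, not whether the sentence is right.

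**Conclusion.** Wrong as written, low impact. The sentence either erases a qualifying event in a man with no evaluable post-baseline scan or, if confined to event-free men, contradicts the latest-date rule before it.

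Three stronger inferences are not supported:

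- A reader might infer that any missed scan or PSA sends a man to time zero. The triggers require an item to be wholly absent or, for post-baseline scans, never evaluable.
- A reader might infer that all five groups lose events. The no-baseline and no-post-baseline-PSA groups should hold almost none.
- A reader might infer that the arm comparison is biased. The documents give no arm-specific rate of missing scans, and the two leuprolide arms were double-blind on one schedule. Differential loss is possible, not shown.

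The figures of 7 to 36 men and 1 to 11 events rest on assumed shares, not on data in the plan. The endpoint is an other secondary one with descriptive, unadjusted p-values (SAP 6.3), so MFS, OS and the alpha allocation are unaffected.

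**What to change.** Replace the last sentence of SAP 6.3.6 with: *A documented castration-resistance event on any component counts as an event at its date. Event-free patients are censored at randomization only if they have no usable post-baseline assessment of any component (scan, PSA or SSE); all other event-free patients follow the latest-date rule in the preceding sentence, including its new-therapy and missed-PSA limits.* Keeping those limits matters; otherwise event-free men would again have two rules.

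The protocol synopsis places this endpoint at the primary MFS analysis, and protocol 3.1 says that analysis is complete and the study unblinded. The sponsor should therefore:

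1. State which rule was programmed.
2. Report by arm how many men were set to time zero and how many of them had a qualifying event.
3. If any are affected, give the corrected analysis as a supplementary result beside the one already run, and describe it in the clinical study report.

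The cost is one SAP sentence, a count by arm and at most one rerun. No new data are needed.

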6.3.7. Time to Symptomatic Progression

Time to symptomatic progression is defined as the time in months from randomization to development of a skeletal-related event, worsening of disease-related symptoms requiring initiation of a new systemic antineoplastic therapy, or development of adverse events and clinically significant signs and/or symptoms due to loco-regional tumor progression requiring opiate use, surgical intervention or radiation therapy, whichever occurs first. Patients without observed symptomatic progression at the time of analysis will be censored at the last visit date.

6.3.8. Time to First Symptomatic Skeletal Event (SSE)

Time to first symptomatic skeletal event is defined as the time in months from randomization to use of radiation therapy (external beam radiation therapy or radionuclides) or surgery to bone for prostate cancer, findings of clinically apparent pathologic bone fracture or of spinal cord compression, or new use of opiate and/or systemic antineoplastic therapy due to bone pain collected in the SSE CRF, whichever occurs first. Because skeletal events are expected to occur after radiographic progression, the analysis of time to first symptomatic skeletal event will be performed with the final overall survival analysis.

The time to first symptomatic skeletal event will be compared between treatment groups using a 2-sided stratified log-rank test. In patients with no SSE by the time of the data

analysis cut-off date, the time to first SSE will be censored on the last visit date or the date of randomization, whichever occurs last.

At the time of final analysis of OS, this endpoint will be updated and summarized descriptively and provided as exploratory analysis.

6.4. Patient Reported Outcomes

The following analyses will be performed for the ITT population.

6.4.1. Pain

The assessment of pain progression will be conducted using the BBPI-SF questionnaire. For each treatment arm and at each time point, the number and percentage of patients who completed the questionnaire will be summarized.

Time to clinically relevant pain progression is defined as the time in months from randomization to onset of pain progression BPI-SF, where pain progression is defined as a 2-point or more increase from baseline in the question 3 score. Patients without observed pain progression at the time of analysis will be censored at the date of last pain assessment on or before the analysis data cutoff date. Patients who were randomized, but with no baseline or no post baseline scores, or with a score that is too high (>8 in BPI-Item 3) at baseline to be able to show further deterioration, for any of the three previous scenarios, will be censored on the date of randomization.

The assessment of pain progression will be compared between the 2 treatment groups using a 2-sided stratified logrank test.

BPI-SF domain scores and change from baseline will be summarized by treatment arm as randomized. Pain Severity score, will be calculated by averaging the ratings of the four pain severity items (items 3, 4, 5 and 6). All four severity items must have been completed for the mean to be calculated. BPI-SF Pain Interference score is calculated as the average of the seven pain interference items (items 9A-9G). The pain interference score will be calculated if more than 50% of the total items, or four out of seven, have been completed on a given administration.

Subjects with missing baseline scores are not assessable for baseline description or change from baseline. Patients with no baseline scores or no post baseline scores are not assessable for baseline description or change from baseline summaries.

Additional PRO analysis of pain will be described in a supplemental SAP specific to PRO data.

6.4.2. Quality of Life

Quality of life will be assessed using FACT-P, EQ-5D-5L, and QLQ-PR25 questionnaires.

For each treatment arm and at each time point, the number and percentage of patients who completed the FACT-P, EQ-5D-5L, and QLQ-PR25 questionnaires will be summarized. An instrument is considered complete if at least one scale can be computed.

Time to functional status decline (deterioration) by the FACT-P questionnaire is defined as the time in months from randomization until the date of occurrence of a 10-point decrease from baseline in FACT-P total score. Patients without functional status deterioration at the time of analysis will be censored at the date of last FACT-P assessment on or before the analysis data cutoff date. Patients with a score that is too low (<10 in FACT-P total score) at baseline to be able to show further deterioration, or patients with no baseline score, or no post-baseline score, for any of the three previous scenarios, the time to deterioration will be censored at date of randomization.

The time to decline (deterioration) in global FACT-P score will be compared between treatment groups using a stratified 2-sided log-rank test with the same strata as in the time to MFS analysis described in Section 6.1.1.

The FACT-P domain scores and their change from baseline will be summarized by treatment arm as randomized for the ITT population. For handling missing items, if half or more questions within scale are answered then a score will be calculated for that scale. Otherwise the patient score for that scale will be missing. The FACT-P total score is the sum of all 5 subscale scores. The total score will be calculated only if the overall item response rate is greater than 80% (i.e., a minimum of 32 of 39 items currently scored in the FACT-P have been answered), and no subscale scores are missing. FACT-P data will be summarized descriptively by study visit.

For EQ-5D-5L, proportion of patients in each category, EQ-VAS score, and change from baseline will be summarized by treatment arm in the ITT population. On the EQ-5D-5L, questions not answered will be considered as missing items, and will neither be imputed nor utilized. EQ-5D-5L data will be summarized descriptively by study visit.

The QLQ-PR25 domain scores and their change from baseline will be summarized by treatment arm as randomized for the ITT population. The QLQ-PR25 domain scores and total score will be calculated using the EORTC QLQ-C30 Scoring Manual (Fayers 2001). If less than half of the constituent items on the QLQPR25 have been answered for a multi-item subscale, that subscale will be considered missing. Single-item subscales will be considered missing if the constituent item is incomplete. QLQ-PR25 data will be summarized descriptively by study visit.

Subjects with missing baseline scores are not assessable for baseline description or change from baseline.

Additional PRO analyses will be described in a supplemental SAP specific to PRO data.

6.5. Exploratory Endpoint(s)

6.5.1. Progression-Free Survival on First Subsequent Therapy (PFS2)

PFS2 is defined as the time in months from the date of randomization to the first occurrence of investigator-determined disease progression (PSA progression, progression on imaging, or clinical progression) or death due to any cause, whichever occurred first, while the patient was receiving first subsequent therapy for prostate cancer.

PFS2 (months) = [date of event or censoring – start date +1]/30.4375

A patient will be considered to have an event if

1. the patient had objective PD on or prior to the start of the first subsequent antineoplastic therapy, AND had investigator-determined disease progression (PSA progression, progression on imaging, or clinical progression) after the start of the first subsequent antineoplastic therapy)

OR

2. the patient died.

If there are multiple therapies within a regimen with different start dates, the earliest start date will be utilized. PFS2 will be analyzed using a 2-sided stratified log-rank test. The HR and 95% CI will be provided. Kaplan-Meier estimates will be presented by treatment arm with the median and 95% CIs.

The censoring and event date options to be considered for PFS2, each corresponding censoring reason and its hierarchy are presented in Table 9. Frequency (number and percentage) of patients with an event (PSA progression, progression on imaging, clinical progression after next line treatment or death) and censoring reasons will be presented by treatment arm.

Scenario	Date of Event/ Censoring	Event/ Censoring Reason/ Censoring Hierarchy
(No PD ^a) and (no death)	Date of lastadequate tumor assessment ^b documenting no PD	Censored/ No PD/ 1
(No PD ^a) and death	Date of death	Event (Death)
(PD ^a date > NTX ^c start date) and (no death)	Start date of NTX ^c	Censored/

Table 9.Outcome, Event Dates, Censoring Reasons and Hierarchy for PFS2
Analyses

Scenario	Date of Event/ Censoring	Event/ Censoring Reason/ Censoring Hierarchy
		Start of new antineoplastic therapy before PD/ 2
$(PD^a date > NTX^c start date)$ and death	Date of death	Event (Death)
(PD ^a date \leq NTX ^c start date) and (PD2 ^d date is non-missing)	Date of PD2 ^d	Event (PD after start of first subsequent antineoplastic therapy)
(PD ^a date \leq NTX ^c start date) and (no PD	2 ^d) and (no death)	
• If [withdrawal of consent in the end of study page]	Withdrawal of consent date in the end of study page	Censored/ Withdrawal of consent/ 3
• Else if [lost to follow-up in any disposition page]	Last contact date	Censored/ Lost to follow-up/ 4
• Else if no prior conditions are met	Last contact date	Censored/ Ongoing without PFS2 event/ 5
(PD ^a and no NTX ^c) and (no death)	Last contact date	Censored/ Ongoing without PFS2 ^e event/ 6
(PD ^a date \leq NTX ^c start date) and (no PD2 ^d) and death	Date of death	Event (Death)
(PD ^a and no NTX ^c) and death	Date of death	Event (Death)

Table 9.Outcome, Event Dates, Censoring Reasons and Hierarchy for PFS2
Analyses

a. PD is the first objective progressive disease by investigator assessment, without considering any censoring rules

b. If there are no adequate post-baseline assessments, then the censoring date is the date of randomization. If patient has initiated the first subsequent antineoplastic therapy, the last adequate post-baseline assessment on or prior to start date of the first subsequent antineoplastic therapywill be considered.

c. NTX is the first subsequent antineoplastic therapy collected in "Long Term Follow-up Antineoplastic Therapies" CRF page .

d. PD2 is the first progressive disease (PSA progression, progression on imaging, or clinical progression), after initiation of first subsequent antineoplastic therapy by investigator assessment without considering any censoring rules.

5		
Scenario	Date of Event/ Censoring	Event/ Censoring Reason/ Censoring Hierarchy

Table 9.Outcome, Event Dates, Censoring Reasons and Hierarchy for PFS2
Analyses

e. PFS2 is the Progression-Free Survival on First Subsequent Therapy

The PFS2 time or censoring time and the reasons for censoring will also be presented in a patient listing.

At the time of final analysis of OS, this endpoint will be summarized descriptively and provided as exploratory analysis.

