3.3. Exploratory Endpoint(s)

3.3.1. Progression-free survival on first subsequent therapy

Progression-free survival on first subsequent therapy (PFS2) is defined as the time in months from date of randomization to date of investigator-determined disease progression (PSA progression, progression on imaging, or clinical progression) or death due to any cause, whichever occurs first, while the patient was receiving first subsequent therapy for prostate cancer. For censoring rules see Section 6.5.

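### SAP 6.5.1 event rule 1 and Table 9 do not implement the stated PFS2 definition, and they make censoring depend on whether the patient later dies

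*SAP*

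**What the plan says.** SAP 3.3.1 ends PFS2 at the "date of investigator-determined disease progression (PSA progression, progression on imaging, or clinical progression) or death due to any cause", whichever is first, while the patient is on first subsequent therapy. Protocol 9.1.3.11 and 10.4.5 and the opening sentence of SAP 6.5.1 say the same. None of them requires an earlier objective progression.

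SAP 6.5.1 then gives two event rules. Under rule 1 a progression counts only if "the patient had objective PD on or prior to the start of the first subsequent antineoplastic therapy, AND had investigator-determined disease progression" after that therapy began. Under rule 2 any death is an event.

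SAP Table 9 puts these rules into rows. Its footnotes define the terms:
- Footnote a: "PD is the first objective progressive disease by investigator assessment".
- Footnote d: "PD2 is the first progressive disease (PSA progression, progression on imaging, or clinical progression), after initiation of first subsequent antineoplastic therapy".
- Footnote b covers a living patient without objective PD who has started next therapy: "the last adequate post-baseline assessment on or prior to start date of the first subsequent antineoplastic therapywill be considered" as the censoring date.

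A living patient whose objective PD follows NTX start is censored at NTX start, with the reason "Start of new antineoplastic therapy before PD". A living patient with PD on or before NTX and no PD2 is followed to last contact if ongoing ("Ongoing without PFS2 event/ 5"). At the final OS analysis, "this endpoint will be summarized descriptively and provided as exploratory analysis".

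**The concern.** Rule 1 and Table 9 estimate something other than the defined endpoint. Progression on next therapy is what PFS2 is meant to measure, yet it is unused for anyone who starts that therapy before objective PD or never has objective PD.

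The second problem is more basic. For these patients the same history is handled in two ways according to what happens later. If the patient survives to the cutoff, his follow-up ends at or before NTX start. If he dies, his whole follow-up is used and he is an event at death. Kaplan-Meier, log-rank and Cox methods require that censoring at a given time not depend on later outcome.

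At stake are the PFS2 curves, medians and hazard ratio. A reader could not see the problem, because the planned tables give censoring reasons and times but not the progressions dropped or re-dated.

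**Working it through.** **Step 1: row-by-row comparison for patients who start NTX**

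| Patient | Definition | SAP Table 9, alive | SAP Table 9, dead |
|---|---|---|---|
| PD on or before NTX, PD2 recorded | event at PD2 | event at PD2 | event at PD2 |
| PD on or before NTX, no PD2 | no progression event | censored at last contact (withdrawal date if consent withdrawn) | event at death |
| Objective PD after NTX start | event at first PD2, if still on NTX | censored at NTX start | event at death |
| No objective PD, PSA or clinical PD2 | event at PD2, if still on NTX | censored at last adequate scan on or before NTX | event at death |

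The first two rows agree with the definition. The last two do not, and in them the time used depends on later death.

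**Step 2: one patient.** NTX starts at month 30 on PSA rise alone, with PSA progression on NTX at month 42 and no objective PD. Scans are every 24 weeks: 24 × 7 / 30.4375 = 5.52 months. The last scan by month 30 is the fifth: 5 × 5.52 = 27.6 months. The definition gives an event at month 42. Table 9 gives censoring at 27.6 if he is alive, or an event at 80 if he dies at month 80.

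**Step 3: size.** The documents give no PFS2 sample size, power or event count to reproduce, and no share of early starters, so size was examined by simulation over assumed ranges. Both codings were applied to the same simulated patients (120,000 per arm per cell, 165 cells).

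Inputs from the documents:
- control 5-year OS 80%, OS hazard ratio 0.67;
- control median MFS 55 months, MFS hazard ratio 0.58;
- the accrual table in protocol 10.7, with cutoff at 271 deaths among 1068 patients (1068/3 = 356 per arm).

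The hazard of PD or early NTX was taken as MFS hazard minus death hazard:
- Control: ln 2/55 - (-ln 0.80/60) = 0.0126 - 0.0037 = 0.0089 per month.
- Enzalutamide: 0.58 × 0.0126 - 0.67 × 0.0037 = 0.0048 per month.

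Other assumptions: NTX a mean of 2 months after PD in the remaining patients; half of PD2 in early starters seen on imaging; early starters without an event censored at cutoff under the definition coding.

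Varied because the documents are silent: the share of early NTX among patients reaching PD or NTX; PD2 hazard after NTX of 0.005 to 0.08 per month (median 139 to 9 months); death hazard after PD2 of 1, 5 or 10 times that before.

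Table 9 coding minus definition coding:

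| Early share, control/enzalutamide (%) | Control 60-month PFS2 (points) | Hazard ratio |
|---|---|---|
| 0/0 | 0 | 0 |
| 5/5 and 10/10 | -0.1 to +1.9 | -0.007 to 0.000 |
| 10/5 | not listed | -0.008 to +0.015 |
| 5/10 | not listed | -0.017 to -0.003 |
| 20/20 and 40/40 | -0.3 to +8.0 | -0.031 to -0.001 |
| 40/20 | not listed | -0.036 to +0.072 |
| 20/40 | not listed | -0.072 to -0.010 |

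At 5/5 and 10/10, about 9 to 18 control and 6 to 12 enzalutamide patients start early. Of their PD2 events, 2 to 16 and 1 to 11 are dropped or re-dated, which is 1% to 8% of events. The control median moves by -2.3 to +3.2 months. The curves were too low only when progression on NTX was very slow (hazard 0.01 or less, median ln 2/0.01 = 69 months or more); otherwise they were too high.

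**Step 4: scale.** With 218 to 418 PFS2 events in two arms, the standard error of the log hazard ratio is about 2/√events, that is 0.135 to 0.098. Around 0.65 the 95% limits lie 0.11 to 0.15 below and 0.14 to 0.20 above.

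**Step 5: no true difference between arms.** A simpler simulation (356 per arm, 150 runs, median 24 months from NTX to PD2) gave a hazard ratio of 1.00 to 1.02 under the definition. Table 9 gave 0.99 with 25% early starters in both arms, 1.08 with 10% experimental and 30% control, and 0.92 with 50% experimental and 20% control.

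**The case against.** The best counter-argument is about weight. PFS2 is exploratory and carries no alpha. At early shares of 5% to 10% the hazard ratio moves by at most 0.017, far inside its confidence interval. The larger shifts need shares of 20% to 40% that no document supports, and protocol 7.2 and 9.1.3.1 restrict treatment changes before radiographic progression. All of that stands.

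The evidence that early starters are expected is also uneven. Part of MFS Sensitivity 5 (SAP 6.1.1.3) concerns stopping study treatment rather than starting another. It refers to radiographic metastasis, whereas Table 9 uses investigator-assessed objective PD. SAP 6.2.4 expects access to commercial treatment without saying whether before or after PD. Still, Table 9 has its own row for these patients, SAP Table 7 censors therapy started without evidence of metastasis, and Sensitivity 5 names novel androgen inhibitors started before metastasis. PFS2 has no matching sensitivity analysis.

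It can be said that rule 1 is a prespecified operational rule and that SAP Section 2 lets the SAP modify the protocol. That does not cure a conflict between two parts of the SAP, or make outcome-dependent censoring valid.

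Read literally, the definition restricts deaths as well as progressions to time on NTX. The comparison counted every death, following rule 2. The simulation also carves early NTX out of an MFS hazard that, under Table 7, would censor such patients, and it does not treat monotherapy separately. These points limit the precision of the ranges, not the finding.

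**Conclusion.** The concern holds. Rule 1 and Table 9 conflict with the PFS2 definition, and they censor early starters according to whether they later die. The codings differ only for those patients, so with none there is no bias.

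With small, equal shares the curves are usually slightly too high and the hazard ratio hardly moves. A material shift in the hazard ratio needs larger shares that differ by arm, and its direction depends on which arm has more. Equal shares should not be presumed. SAP 5.1.2 reports that results so far allow OS to be tested at 0.05, which under 5.1.3 requires significant differences in time to PSA progression and time to new antineoplastic therapy in both comparisons. That shows timing differs by arm; it does not give the share starting before PD.

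This should be corrected, but it does not threaten a confirmatory conclusion. The conflict rests on the text alone. The sizes rest on the assumptions listed.

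**What to change.** Keep Table 9 as prespecified and add to SAP 6.5.1, reported beside it, a PFS2 analysis coded to the definition:
- Event: first PD2 of any type on first subsequent therapy, or death, whether or not objective PD came first.
- Censoring: every NTX starter without an event is treated as Table 9 already treats patients with PD on or before NTX, that is at last contact (or the withdrawal date where consent is withdrawn). The definition has no censoring rule, so say that this one is borrowed.
- State how progressions recorded after the first subsequent therapy has stopped are handled, and confirm that all deaths count.
- Tabulate by arm the patients starting NTX before or without objective PD, and the PD2 events that Table 9 drops or re-dates to death.

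The cost is a little programming. Subsequent therapies and the dates of progression on the first of them are already collected (protocol 5.5, Table 9; protocol 18.8, Table 18). The drawback is that the study is already unblinded (protocol 3.1), so the analysis must be labelled as specified after unblinding. If early starters prove rare, the count will show it and settle the matter.
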